# 4.2.2.2 Intravenous Dosing

Crenezumab will be given by IV infusion once every 4 weeks. Missed treatments will not be made up.

For IV use, the drug will be diluted as described in the *GN28525* pharmacy manual. The IV drug will be administered

. IV infusions will be administered by the site staff in a hospital, clinic, or practice environment. All patients will be followed for a minimum of 1 hour postdose and vital signs will be measured post-infusion and 60 minutes after the end of the infusion as described in the GN28525 pharmacy manual.

For IV dose calculation in the OLE study, the screening weight refers to the patient's weight at Week 73. For patients who entered GN28525 immediately upon completion of

Crenezumab—Genentech, Inc. 46/Protocol GN28525, Version 6 ABE4869g or ABE4955g, the IV dose will be calculated based on the patient's screening weight (reference weight) unless the patient's current weight changes (increases or decreases)  $\geq$  10% from the screening weight. For patients who will be transitioned from SC dosing to IV dosing during the conduct of GN28525, the IV dose will be calculated based on the patient's current weight at the time of transition (their reference weight). For all patients, whether originally in the IV cohort or transitioning from the SC cohort, if the current weight changes  $\geq$  10%, the current weight will become the new reference weight for subsequent dosing. If the patient's weight again changes by  $\geq$  10% from the reference weight, the IV dose will again be recalculated. Please refer to the *GN28525* pharmacy manual for further information.

If a patient experiences a mild infusion-related reaction, the infusion will be halted. Once the reaction has resolved, the infusion will be resumed at half of the most recently used rate **Constitution**. Patients who experience a moderate infusion-related reaction (e.g., fever, chills) should have their infusion stopped immediately and should receive aggressive symptomatic treatment. The infusion should not be restarted before all symptoms have disappeared, and then it should be restarted at half the initial rate. Patients who experience serious or severe hypersensitivity reactions (e.g., hypotension, mucosal involvement), should have their infusion stopped immediately and should receive aggressive symptomatic treatment, and they should not receive additional study drug.

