# 4.2.1 Formulation, Packaging, and Handling

# 4.2.1.1 Crenezumab (MABT5102A)

Crenezumab is produced using Chinese hamster ovary cells, purified, and formulated. Crenezumab is subjected to a series of quality-control tests to confirm its identity, purity, potency, quality, and sterility. The drug product is a sterile, preservative-free liquid intended for SC or IV administration.

Details on crenezumab *and placebo* formulation, dosage, *configuration*, administration, and storage are provided in the crenezumab (MABT5102A) Investigator's Brochure and *the GN28525* pharmacy manual.

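### The restart rule after a moderate infusion reaction has no visible cap, so an infusion that has already been slowed can restart with no reduction in rate

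*Combined protocol and SAP*

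**What the plan says.** Section 4.2.2.2 sets out three responses to an infusion reaction.

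- **Mild:** the infusion is halted, and "Once the reaction has resolved, the infusion will be resumed at half of the most recently used rate".
- **Moderate:** "Patients who experience a moderate infusion-related reaction (e.g., fever, chills) should have their infusion stopped immediately and should receive aggressive symptomatic treatment". The next sentence sets the restart: "The infusion should not be restarted before all symptoms have disappeared, and then it should be restarted at half the initial rate".
- **Serious or severe hypersensitivity:** patients "should have their infusion stopped immediately and should receive aggressive symptomatic treatment, and they should not receive additional study drug".

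The moderate-reaction sentence is complete and has no gap. The rate at which the drug is normally infused is blacked out, and a short stretch after the mild rule is damaged. Section 4.2.1.1 refers the reader to the Investigator's Brochure and the pharmacy manual for details that include administration.

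**The concern.** The section grades its response by severity: halt for mild, stop and treat for moderate, no further drug for serious or severe. The two restart rules do not share a reference rate. The mild rule follows the current rate down, while the moderate rule is tied to the rate at the start of the infusion. Once an infusion has been slowed, the worse reaction can therefore get the faster restart, and the restart may be no slower than the rate that provoked the reaction.

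What is at stake is infusion safety in patients who react more than once. Section 1.3.6 lists hypersensitivity reactions and anaphylaxis among the potential safety considerations. All patients formerly dosed subcutaneously, and former placebo patients, now receive 15 mg/kg intravenously. Dosing every 4 weeks from Week 1 to Week 145 allows up to (145 − 1)/4 + 1 = 37 infusions per patient. The statistical analysis is not affected.

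**Working it through.** The plan states no figure to reproduce, so the check is arithmetic on the two rules.

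**Inputs**

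- R: the initial rate, read as the rate at the start of the infusion. Its value is not needed.
- k: the rate in use before the first reaction, divided by R. This is blacked out. Assumed values are k = 1 (constant rate), 2 and 4 (stepped-up rates).
- n: the number of earlier mild reactions in the same infusion, each halving the rate.

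**Formulas, in units of R**

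- Provoking rate = k/2^n
- Mild restart = k/2^(n+1)
- Moderate restart = 0.5

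The moderate restart is faster than the mild one when 0.5 > k/2^(n+1), that is, when k < 2^n. It gives no reduction from the provoking rate when 0.5 ≥ k/2^n, that is, when k ≤ 2^(n−1).

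The last column is the lower of 0.5 and k/2^(n+1), the rule proposed as the fix.

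| k | n | Provoking rate | Mild restart | Moderate restart | Moderate ÷ provoking | Lower-of rule |
|---|---|---|---|---|---|---|
| 1 | 0 | 1 | 0.5 | 0.5 | 0.5 | 0.5 |
| 1 | 1 | 0.5 | 0.25 | 0.5 | 1 | 0.25 |
| 1 | 2 | 0.25 | 0.125 | 0.5 | 2 | 0.125 |
| 2 | 0 | 2 | 1 | 0.5 | 0.25 | 0.5 |
| 2 | 1 | 1 | 0.5 | 0.5 | 0.5 | 0.5 |
| 2 | 2 | 0.5 | 0.25 | 0.5 | 1 | 0.25 |
| 2 | 3 | 0.25 | 0.125 | 0.5 | 2 | 0.125 |
| 4 | 0 | 4 | 2 | 0.5 | 0.125 | 0.5 |
| 4 | 1 | 2 | 1 | 0.5 | 0.25 | 0.5 |
| 4 | 2 | 1 | 0.5 | 0.5 | 0.5 | 0.5 |
| 4 | 3 | 0.5 | 0.25 | 0.5 | 1 | 0.25 |

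With no earlier slowdown (n = 0) the moderate rule matches the mild one at k = 1 and is stricter at k = 2 and 4. The restart first equals the provoking rate after one earlier slowdown at k = 1, two at k = 2 and three at k = 4.

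**Repeat moderate reaction.** The first moderate reaction sets the rate to 0.5R whatever k is. If the rate is not raised afterwards, a second one is provoked at 0.5R and restarts at 0.5R, a reduction of 0%. A mild reaction at the same point would restart at 0.25R. The visible text does not say whether the rate may be raised after a restart.

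**The case against.** The strongest case on the other side is that the defect depends on things the reader cannot see.

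- **The planned rate is blacked out.** With a step-up to twice the initial rate, one earlier slowdown only makes the two rules tie. At four times, the moderate rule is still stricter after one slowdown and ties after two. The repeat-moderate case does not depend on k, but it does require that the rate is not raised again, and a stepped schedule might allow that.
- **The pharmacy manual may contain a cap.** Section 4.2.2.2 cites the manual for dilution, vital signs and weight-based dosing, but Section 4.2.1.1 refers to it for administration in general.
- **The term may mean something else.** If *initial rate* means the rate in use when the reaction began, the two rules agree.
- **The situation may be rare.** It needs at least two reactions, the later one moderate, with the slower rate still in force. The immediate stop, the treatment and the wait for all symptoms to clear still apply, as does at least 1 hour of observation after dosing.

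All four points stand as limits on size and certainty. They do not remove the fault in the written rule. The moderate-reaction sentence is not redacted and carries no lower-of limit. The mild rule just before it uses a different term for the current rate, which favours reading *initial rate* as the starting rate. If the other meaning was intended, a safety instruction is ambiguous and the same edit resolves it. If the manual has a cap, the protocol gives site staff a different number and should be aligned with it.

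**Conclusion.** The concern holds on the readable text, as a minor point with medium confidence. At a constant rate, one earlier slowdown is enough for a moderate reaction to restart at the provoking rate, twice the mild restart. Two earlier slowdowns give a restart at double the provoking rate and 0.5/0.125 = 4 times the mild restart. A stepped-up rate needs more slowdowns before this happens. A repeat moderate reaction gives no reduction at any k, provided the rate was not raised in between.

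This rests on reading *initial rate* as the starting rate, on assumed values of k, and on there being no cap in the blacked-out text or the pharmacy manual. The gap is confined to the restart rate in patients with repeat reactions, whose number the documents do not give.

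**What to change.** In Section 4.2.2.2, change the moderate-reaction restart to *half the initial rate or half the most recently used rate, whichever is lower*. Align the pharmacy manual if it repeats the rule.

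Because the lower-of rule never exceeds k/2^(n+1), the moderate restart is never faster than the mild one and is always at least 50% below the provoking rate, for every k and n. It never loosens the present rule. A single common reference does not work. Using the initial rate for both reactions leaves the fault in place. Using the most recent rate for both weakens the moderate rule after a step-up: at k = 2 with no earlier slowdown, the restart would be 1R instead of 0.5R.

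The cost is one clause, plus a longer remaining infusion for patients with repeat reactions. At k = 1 the remaining time is 0.5/0.25 = 2 times that under the present rule after one earlier slowdown, and 0.5/0.125 = 4 times after two. In the latter case the rate is one-eighth of the starting rate, so the remaining volume takes 8 times as long as at the starting rate. The product is preservative-free (Section 4.2.1.1), so the sponsor should check this against any in-use time limit for the diluted drug, which the documents do not show. Sample size, visits and analysis do not change.

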# 4.2.3 Investigational Medicinal Product Accountability

All investigational medicinal products (IMPs) required for completion of this study will be provided by the Sponsor where required by local health authority regulations. The investigational site will acknowledge receipt of IMPs by returning the appropriate documentation form to confirm the shipment condition and content. Any damaged shipments will be replaced.

IMPs will either be disposed of at the study site according to the study site's institutional standard operating procedure or returned to the Sponsor with the appropriate documentation. The site's method of IMP destruction must be agreed to by the Sponsor. The site must obtain written authorization from the Sponsor before any IMP is destroyed, and IMP destruction must be documented on the appropriate form.

Accurate records of all IMPs received at, dispensed from, returned to, and disposed of by the study site should be recorded on the Drug Inventory Log.

#### 4.2.4 Post-Trial Access to Crenezumab

The Sponsor does not intend to provide crenezumab or other study interventions to patients after conclusion of the study or any earlier patient withdrawal.

# 4.2.5 Permitted Therapy

Concomitant therapy includes any medication (e.g., prescription drugs, over-the-counter drugs, herbal or homeopathic remedies, nutritional supplements) used by a patient from the day of study enrollment (Day 1) through study completion or early termination. All concomitant medications should be reported to the investigator and recorded on the Concomitant Medications eCRF.

Except for excluded medications, patients who use other maintenance therapies may continue their use (see Section 4.1.2).

Patients are permitted to take approved Alzheimer's disease treatments (e.g., AChE inhibitors, and memantine). An approved Alzheimer's disease treatment may be initiated, stopped, or altered in dose or formulation up to, and including, the Week 13 visit. If an approved Alzheimer's disease treatment is no longer commercially available or no longer available through patients' insurance formulary, the treatment may be substituted with an equivalent dose of a comparable medication at any time during the trial. Stable doses of other maintenance medications will also be permitted. The intermittent use of opiates, opioids, soporifics, or benzodiazepines is allowed, except within 5 half-lives prior to any neurocognitive assessment (see Section 4.1.2).

Chronic treatment with benzodiazepines, opiates, or opioids is prohibited; however, intermittent, short-term treatment is allowed except within 5 half-lives prior to any neurocognitive assessment.

Non-excluded prescription and over-the-counter medications (see Section 4.1.2) that might affect cognitive function (e.g., non-anticholinergic antidepressants, atypical antipsychotics, non-benzodiazepine anxiolytics, soporifics, centrally acting anticholinergic antihistamines, centrally acting anticholinergic antispasmodics) are allowed a) if initiation or discontinuation of therapy or dose changes do not occur within 5 half-lives prior to cognitive assessment (however, initiation, discontinuation, or dose changes are discouraged), or b) administered intermittently and on a short-term basis, they are not used within 5 half-lives prior to neurocognitive assessment.

During the study, patients may receive any treatment deemed necessary by the investigator for the management of their disease. However, patients requiring commencement of prohibited therapies will be discontinued from the study.

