### 3. STUDY DESIGN

## 3.1 DESCRIPTION OF STUDY

### 3.1.1 Overview of Study Design

Study GN28525 is a Phase II, OLE, multicenter study to evaluate the long-term safety and tolerability of crenezumab in patients with Alzheimer's disease who have participated in and completed the treatment period of the Phase II Study ABE4869g or ABE4955g. Patients from Studies ABE4869g and ABE4955g who discontinued from study treatment early but remained on study for safety evaluations, or discontinued prior to completion of the Week 73 study visit, are not eligible for this OLE study.

ABE4869g (ABBY) is a completed Phase II, multicenter, global, randomized, double-blind, parallel-group, placebo-controlled study to evaluate the safety and efficacy of crenezumab in patients with mild-to-moderate Alzheimer's disease. Four hundred forty-six patients were randomized and 444 patients were dosed at approximately 100 sites in North America and Europe.

ABE4955g (BLAZE) is a completed Phase II, multicenter, global, randomized, double-blind, parallel-group, placebo-controlled study to evaluate the effects of crenezumab on brain amyloid burden, as assessed by florbetapir-PET, and other biomarkers in patients with mild-to-moderate Alzheimer's disease. Ninety-one patients were randomized and 61 were dosed at approximately 30 sites in North America and Europe.

This OLE study includes patients who have been diagnosed with Alzheimer's disease and have an MMSE score of 10 or more at the time of screening, which is lower than in Studies ABE4869g and ABE4955g (MMSE 18 – 26) to account for the disease progression in the course of these studies. An MMSE score of less than 10 at the beginning of the OLE study would substantially increase the risk that a patient would not be able to complete the study assessments and to comply with the protocol's requirements in the future.

Patients will undergo a neuroradiological evaluation using a standard MRI protocol and T2\* gradient echo MRI to exclude any significant MRI abnormality and presence of cerebral superficial siderosis or more than eight cerebral microhemorrhages. Only

Crenezumab—Genentech, Inc. 38/Protocol GN28525, Version 6

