The study consists of three periods: a screening period (up to 14 days), the window between the last dose in ABBY/BLAZE and the first dose in OLE may last 6 weeks, but may be prolonged on a case by case basis for relevant clinical, administrative, or operational reasons (these reasons must be discussed with the medical monitor in advance of screening; if necessary, some screening procedures may need to be repeated); a treatment period of 144 weeks (Week 1 [Day 1] to Week 145), and an 8-week safety follow-up period (Weeks 145 to 153). The final safety analysis will be performed at 153 weeks. The original GN28525 protocol included a treatment period of 92 weeks (Week 1 [Day 1] to Week 93). Version 6 of the GN28525 protocol expands this treatment period by 52 weeks (13 additional IV doses from Week 97 to Week 145). Patients who are still enrolled in Study GN28525 may enter the additional OLE treatment period (Week 145) if they have not discontinued treatment for

Crenezumab—Genentech, Inc. 39/Protocol GN28525, Version 6

[figure not shown]
safety reasons. Patients who have already completed or discontinued from Study GN28525 are not eligible to receive additional treatment from Week 97 to Week 145.

The Week 73 assessment (including MRI) of Studies ABE4869g and ABE4955g will be used to determine the patient's eligibility in this OLE trial. Data from the Week 73 visit assessments in Studies ABE4869g and ABE4955g will be extracted and incorporated in the OLE screening datasets. Patients participating in this OLE study must be enrolled (i.e., Day 1 of the OLE treatment period) no later than 14 days after completion of the Week 73 assessments (including MRI) of Study ABE4869g or ABE4955g, except for individual exceptions, determined on a case by case basis, as mentioned above.

The first dose of crenezumab is administered on Day 1 of the treatment period, and the last dose of treatment is at Week 145. After patients complete the 144-week treatment period, they will enter the follow-up period. Patients who are prematurely discontinued from the OLE study treatment will also discontinue from the OLE study and will be followed for safety for 8 weeks after their last dose of crenezumab.

Patients will remain blinded to their assignment in Study ABE4869g or ABE4955g, and investigators are not permitted to provide treatment assignment in ABE4869g or ABE4955g until permitted by the Sponsor.

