# 4.2.6 Prohibited Therapy

Use of the following therapies is prohibited during the study, unless otherwise specified below:

- Anticholinergic antidepressants, typical antipsychotics, or barbiturates
  - All other antidepressants and atypical antipsychotics are allowed with certain limitations (see Section 4.2.5).

- Anticoagulation medications (e.g., heparin, warfarin, thrombin inhibitors, Factor Xa inhibitors)
  - Clopidogrel, dipyridamole, and aspirin are permitted.
- Any biologic therapy
  - Routinely recommended vaccinations are allowed.
- Any investigational agent

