# 4.4.2 Study Treatment Discontinuation

Patients with a serious, life-threatening adverse event, superficial siderosis of central nervous system, one new cerebral macrohemorrhage, an increase by one or more in the number of symptomatic cerebral microhemorrhages compared with screening, or an increase by six or more in the number of asymptomatic cerebral microhemorrhages compared with screening, as assessed by T2\*-weighted GRE MRI, must not receive additional doses of crenezumab, and must be discontinued from the study treatment.

The primary reason for study treatment discontinuation should be documented on the appropriate eCRF. Patients who discontinue study treatment prematurely will not be replaced.

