#### 5.1.3 Pneumonia

As described in Section 1.3.3, in the RPCP of Phase II clinical trials in mild-to-moderate Alzheimer's disease (ABBY and BLAZE), there was an imbalance in the rates of pneumonia, with 3.2% (11/346) of crenezumab-treated patients and 0.6% (1/176) of patients on placebo having pneumonia. Of these 12 pneumonia cases, 7 were assessed as serious (4 on crenezumab IV, 2 on crenezumab SC, and 1 on placebo).

The rate of pneumonia in crenezumab-treated patients (3.2%) is within the reported incidence of pneumonia in the elderly population (2.5%-4.4%) (Chong et al. 2008), but rates (both total and serious) are slightly higher in crenezumab-treated patients (3.2%) and slightly lower in placebo-treated patients (0.6%) than rates reported in the active and placebo arms of clinical trials in Alzheimer's disease (Doody et al. 2014; Henley et al. 2014; Salloway et al. 2014). There is no clinical evidence of immunosuppression (e.g., effects on white blood cells or neutrophils; or pattern of infection type, e.g., opportunistic infections). In addition, no evidence of immunosuppression or of a lung toxicity effect has been observed in preclinical studies. Based on the currently available data, a causal relationship between the drug and events of pneumonia cannot be established or ruled-out. Pneumonia is considered a potential risk and will be monitored closely.

Pneumonia is now considered an adverse event of special interest and should be reported in an expedited manner (see Section 5.2.3).

Patients with signs and/or symptoms suggestive of pneumonia (e.g., cough, fever, pleuritic chest pain) should undergo chest radiography for confirmation of diagnosis. Additional tests might be considered at the discretion of the treating physician. Patients should be treated as per the standard treatment of care, and any change to study drug should be considered within a benefit/risk assessment frame and be in agreement with the Medical Monitor.

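### Needing a prohibited drug ends study participation: safety follow-up shortens, the off-drug Week 153 visit is forfeited, and exits triggered by an adverse event have no attribution rule

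*Combined protocol and SAP*

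**What the plan says.** Section 4.2.5 first allows any treatment the investigator finds necessary for the patient's disease, then adds: "However, patients requiring commencement of prohibited therapies will be discontinued from the study". The consequence is loss of the study, not only of study drug. Section 4.2.6 lists, for the duration of the study, "Anticholinergic antidepressants, typical antipsychotics, or barbiturates" and "Anticoagulation medications (e.g., heparin, warfarin, thrombin inhibitors, Factor Xa inhibitors". It permits some alternatives (atypical antipsychotics with limits, clopidogrel, dipyridamole, aspirin). It has no exception for short courses or for a drug given to treat an AE.

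Other sections bear on what happens next:

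- **Section 3.1.1 and the Synopsis:** a patient prematurely taken off treatment, for any reason, "will also discontinue from the OLE study and will be followed for safety for 8 weeks after their last dose of crenezumab".
- **Section 4.4.1:** a patient leaving the treatment period before Week 145 is asked to attend an early-termination visit within 4 weeks of the last dose and a further safety visit 8 weeks after that. One primary reason for withdrawal is recorded.
- **Section 4.4.2:** patients with certain safety findings "must not receive additional doses of crenezumab, and must be discontinued from the study treatment". Starting a concomitant drug is not among those findings.
- **Section 5.1.3:** after pneumonia, "any change to study drug should be considered within a benefit/risk assessment frame and be in agreement with the Medical Monitor".
- **Section 6.2:** discontinuations and their reasons are tabulated. No rule says how to code an exit in which an AE led to a prohibited drug.

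**The concern.** The primary objective is long-term safety. A drug on the Section 4.2.6 list may be started because an AE has occurred, and Section 4.2.5 then ends participation. Length of observation thus becomes a function of the outcome. Later events and six-monthly MRIs are lost for patients who have just had an event, and any long-term rate leans towards those who stayed well.

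Two narrower gaps follow:

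- The ban runs throughout the study, so it also covers the eight weeks after the last dose. No study drug is left to stop in that period.
- With one primary reason and no attribution rule, sites may code the same clinical sequence either as an AE or as prohibited therapy.

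**Working it through.** **1. The plan's own figures.** Timeline: 92 + 52 = 144 weeks of treatment; Week 145 + 8 = Week 153. AE discontinuations in the placebo-controlled portion (Section 1.3.3.2): crenezumab 2 + 8 + 1 + 1 = 12, and 12/346 = 3.5%; placebo 3 + 3 + 0 + 4 = 10, and 10/176 = 5.7%. All agree with the text.

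**2. Follow-up lost by an early leaver.** For a last dose at Week w, follow-up ends at w + 8 (Section 3.1.1) or as late as w + 4 + 8 = w + 12 (Section 4.4.1). Planned follow-up from Week 1 to Week 153 is 152 weeks. Weeks lost = 153 − (w + 8), or 153 − (w + 12).

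| Last dose | Follow-up ends | Weeks lost | Share of 152 |
|---|---|---|---|
| Week 25 | Week 33 or 37 | 120 or 116 | 79% or 76% |
| Week 73 | Week 81 or 85 | 72 or 68 | 47% or 45% |
| Week 121 | Week 129 or 133 | 24 or 20 | 16% or 13% |

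**3. The off-drug period.** Take a patient dosed at Week 145 who needs a listed drug at Week 147. Section 4.2.6 still applies, and Section 4.2.5 discontinues the patient from the study. The early-termination visits in Section 4.4.1 cover only exits before Week 145, so no replacement visit is stated. Section 6.2 defines completion through Week 153, and Sections 6.4.2 and 6.4.4 summarise laboratory and antibody results at Week 153. Dosing is unaffected; only those data are lost.

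**4. Attribution.** Section 1.3.3.5 gives, at 27 May 2014, AE discontinuations in 8 SC patients (5.4%) and 2 IV patients (0.9%). The denominators are not stated. The SC percentages (15 = 10.1%, 8 = 5.4%, 6 = 4.1%) fit only n = 148. The IV percentages (18 = 8.5%, 2 = 0.9%, 3 = 1.4%) fit n = 211 to 213. The total is about 360, and 10/360 = 2.8%. Suppose m further exits were AE-driven but coded as prohibited therapy (assumption; the documents give no count). The share would be (10 + m)/360:

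- m = 2: 3.3%
- m = 5: 4.2%
- m = 10: 5.6%

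**5. Illustration for the fatality comparison (Sections 1.3.3.5 and 5.1.4); all inputs assumed.** Let the death hazard be h = 1 to 2 per 100 patient-years. A share f = 2% to 10% has a last dose at Week 73, with hazard k·h afterwards (k = 1 to 5). At constant hazard, deaths over t weeks are 1 − exp(−ht/52) and person-years are that quantity divided by h. Compare leavers followed for 80 further weeks (to Week 153) with leavers followed for 8. At h = 1, f = 10%, k = 5, the rates are 1.20 and 1.02 per 100 patient-years, a ratio of 0.85. At k = 1 the ratio is 1.00. Across the grid the truncated rate is 0.85 to 1.00 of the full one. This counts all observed time, whereas Section 1.3.3.5 uses time on crenezumab, so it shows direction only.

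**The case against.** The best defence is that the plan already protects these patients' data. Early leavers have safety follow-up. All AEs are reported for at least 8 weeks after the last dose (Section 5.3.1). Each AE is followed to resolution or stability (Section 5.5.1). Everyone with one dose stays in the safety set (Section 6.4). AE frequency and severity are defined for the treatment period (Section 3.4.1), and the fatality rate uses time on drug, so visits off drug would add little to either. All of this stands and limits the point.

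A reader might infer more than the documents support:

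- *That safety follow-up ends at exit.* It is shortened.
- *That the loss is peculiar to prohibited drugs.* Section 3.1.1 ends participation after any premature treatment stop, so editing Section 4.2.5 alone would not restore follow-up before Week 145.
- *That the AE-discontinuation count is cut.* No text directs coding away from the AE. Attribution is undefined and could move the count either way; nor is this count a listed primary outcome.
- *That the 0.9% for IV patients shows how fragile the count is.* The same sentence gives 5.4% for SC patients.
- *That the number of exits can be projected from serious-AE rates.* The documents give no frequency of listed-drug starts, and patients who had already completed or discontinued do not enter Weeks 97 to 145.
- *That Sections 5.1.3 and 4.4.2 flatly contradict Section 4.2.5.* Section 5.1.3 is silent on concomitant drugs, and the withdrawal reasons in Section 4.4.1 are expressly not exhaustive. Likewise, a two-week washout at entry is compatible with a ban on concurrent use.
- *That every such patient should attend all visits and MRIs to Week 153.* The feeder studies had patients who "discontinued from study treatment early but remained on study for safety evaluations", so it is feasible, but here it is a debatable design trade-off.

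For Weeks 145 to 153 it can also be said that nothing expressly cancels the visit and AE reporting continues. But a patient discontinued from the study has no stated basis for attending.

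**Conclusion.** The point holds in a limited form. Section 4.2.5 does not separate study drug from study participation and has no exception for drugs given to treat an AE. Observation is therefore shortened in response to events, to about 8 to 12 weeks after the last dose. The loss per patient ranges from about 13% to 79% of planned follow-up for last doses between Week 121 and Week 25. In Weeks 145 to 153 the literal effect is only to forfeit Week 153 data. Attribution of AE-triggered exits is undefined, against a base of 10 of about 360 (2.8%); that denominator is inferred from rounded percentages.

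The total effect cannot be computed, because the number of patients starting a listed drug is not given. Any bias in late-event rates is downward if leavers carry excess risk and nil if they do not. The visit-schedule appendices were not in the text available for this check.

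**What to change.** 1. In Section 4.2.5, state that starting a listed drug after the last dose does not end study participation, so the scheduled Week 153 safety visit still takes place.
2. In Section 4.4.1 and the eCRF instructions, state that when a listed drug was started to treat an AE, that AE is the primary reason for discontinuation. Count these exits with AE discontinuations in Section 6.2, and also tabulate them separately.
3. Reconcile the Synopsis and Sections 3.1.1, 4.2.5, 4.4.1, 4.4.2 and 5.1.3 on what starting a listed drug does to dosing and, separately, to study participation. Which dosing rule applies is for the sponsor; no position is taken here.
4. Reconcile the post-exit rules. Section 3.1.1 counts 8 weeks from the last dose, Section 4.4.1 counts 8 weeks from the early-termination visit. After the 8-week window, Section 5.3.1 asks for deaths, serious AEs and AEs of special interest without a relatedness condition, while Section 5.6 asks only for events believed related.

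The cost is amendment wording, one coding instruction and one extra table. The Week 153 visit is already scheduled, so no procedure is added.
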